#### **10.1.6    *The BMS-986218 Combination-Therapy Cohort Expansion in MSS CRC (Part 2D)***

The purpose of the BMS-986218 Cohort Expansion - Combination Therapy (Part 2D) is to gather additional data including safety, tolerability, preliminary efficacy as combination therapy of BMS-986218 in combination with nivolumab, in participants with MSS CRC. The sample size calculation will be based on the ORR.

Approximately 40 response-evaluable participants will be treated in Part 2D, with the goal of treating approximately 20 participants each with either mutation or wild-type with respect to extended RAS status. As response to immunotherapy may differ substantially based on tumor genomics, ORR will be analyzed separately for participants with mutation and participants with wild-type.

With 20 treated participants with either mutation or wild-type, the lower limit of the 2-sided 80% Clopper Pearson confidence interval for ORR estimate will be 9%, 5.6%, or 2.7%, assuming ORR estimate size of 20%, 15%, or 10%, respectively.

## 10.2 Populations for Analyses

For purposes of analysis, the populations in are defined in Table 10.2-1.

**Table 10.2-1: Population for Analyses**

Population	Description
Enrolled	All participants who sign informed consent and are registered into the IRT
Treated	All participants who take at least 1 dose of study treatment
Randomized	All participants who were randomized to study drug (Parts 2A or 2B)
Response-evaluable	All treated participants with measurable disease at baseline and 1 of the following: (a) at least 1 post baseline tumor assessment, (b) clinical progression, (c) death
Pharmacokinetic	All treated participants who have evaluable concentration-time data
Immunogenicity	All treated participants who have baseline and at least 1 post baseline pre-infusion immunogenicity assessment

## 10.3 Statistical Analyses

The statistical analysis plan will be developed and finalized before database lock, and below is a summary of planned statistical analyses of the primary and secondary endpoints.

A description of the participant population will be included in the statistical output reported, including subgroups of age, gender, and race.

### 10.3.1 Efficacy Analyses

The primary efficacy analyses (Table 10.3.1-1) will be performed on the randomized population in Parts 2A, and 2B, and on all treated participants in Part 1A, Part 1B, Part 2C, and Part 2D, for the final analysis. Supplemental analysis on All treated population may be provided in Parts 2A and 2B; Efficacy analyses based on the response-evaluable population may be performed for interim analyses when the minimum follow-up period is less than sufficient to warrant adequate interpretation of the result. Details of the censoring scheme on time-to-event endpoints such as DOR, progression-free survival rate (PFSR), PID, and overall survival rate (OSR) will be described in the Statistical Analysis Plan.

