**Table 10.3.1-1: Efficacy - Statistical Analyses**

Endpoint	Statistical Analysis Methods
ORR is defined as the proportion of all treated participants whose BOR is either CR or PR by Investigator per RECIST v1.1 or per PCWG 3 criteria for prostate.  BOR for a participant will be assessed per RECIST v1.1 by Investigator, unless otherwise specified.	Estimate of ORR and corresponding 2-sided exact 95% CI using the Clopper-Pearson method by treatment for each tumor type.  For part 2A, estimate of difference in ORR between arms (using ipilimumab as reference) and corresponding 2-sided exact 95% CI using the Clopper-Pearson method by BMS treatment arms.
Median DOR  DOR for a participant with a BOR of CR or PR is defined as the time between the date of first response and the date of the first objectively documented tumor progression per RECIST v1.1 or per PCWG 3 criteria for prostate, or death, whichever occurs first.	Estimate by the Kaplan-Meier method and corresponding 2-sided 95% CI using Brookmeyer and Crowley methodology (using log-log transformation) by treatment for each tumor type.
PFSR at 24, 36, and 48 weeks  PFS for a participant is defined as the time from the first dosing date to the date of first objectively documented disease progression or death due to any cause, whichever occurs first.	Estimate PFSR by the Kaplan-Meier method and corresponding 2-sided 95% CI using Greenwood formula by treatment for each tumor type.  For part 2A, estimate difference in PFSR between arms (using ipilimumab as reference) by the Kaplan-Meier method and corresponding 2-sided 95% CI using Greenwood formula by BMS treatment arms.  Estimate median PFS by the Kaplan-Meier method and corresponding 2-sided 95% CI using Greenwood formula by treatment for each tumor type.

Abbreviations: BOR = best overall response; BMS = Bristol Myers Squibb; CI = confidence interval; CR = complete response; DOR = duration of response; ORR = objective response rate; PCWG 3 = Prostate Cancer Working Group; PFSR = progression-free survival rate; PR = partial response; RECIST = Response Evaluation Criteria in Solid Tumors.

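### Section 10.3.1 makes the randomized population primary for Parts 2A and 2B, but the table it cites defines ORR over treated participants and PFS from first dose

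*Combined protocol and SAP*

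**What the plan says.** Section 10.3.1 sets the population for the final analysis: "The primary efficacy analyses (Table 10.3.1-1) will be performed on the randomized population in Parts 2A, and 2B". The other parts (1A, 1B, 2C, 2D) use treated participants. For the two randomized parts the treated set has a secondary role: "Supplemental analysis on All treated population may be provided in Parts 2A and 2B".

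Table 10.2-1 keeps the two sets apart. The Randomized population carries no dosing condition. The Treated population is "All participants who take at least 1 dose of study treatment".

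Table 10.3.1-1, which the population sentence cites, then defines the endpoints:

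- ORR: "ORR is defined as the proportion of all treated participants whose BOR is either CR or PR by Investigator per RECIST v1.1".
- PFS: "PFS for a participant is defined as the time from the first dosing date to the date of first objectively documented disease progression".

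The table has separate entries for the Part 2A differences from ipilimumab in ORR and in PFS rate (PFSR). Neither changes the denominator or the time origin. Part 2B has by-treatment estimates only.

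Section 10.1.3 adds a third description. It speaks of randomizing 132 response-evaluable participants but bases precision on 33 treated per arm. Under Table 10.2-1, response-evaluable participants are a subset of the treated.

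**The concern.** Someone randomized but never dosed belongs to the primary population, falls outside the ORR definition and has no date from which PFS can start. An analyst who programs from the table would produce the analysis that Section 10.3.1 calls supplemental.

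Such participants are foreseeable. Under Section 7.4, assignment through the IRT follows confirmation of eligibility and so comes before dosing. That section rules out replacement after dosing but is silent on participants who never start. Section 7.5 describes an open-label study, so the assigned arm can influence who starts.

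Efficacy relative to ipilimumab is a primary objective of Part 2A (Table 4-1), with ORR and PFSR among its endpoints. These are the contrasts that randomization is there to protect.

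**Working it through.** **1. The rules applied to one participant randomized but never dosed**

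- Section 10.3.1 and Table 10.2-1: in the primary population.
- ORR in Table 10.3.1-1: not in the denominator.
- PFS in Table 10.3.1-1: no start date.

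The three cannot hold together. Section 10.3.1 leaves the censoring scheme to the later SAP, but it does not leave the denominator or the time origin open.

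**2. The plan's own figures**

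Section 10.1.3 gives lower 1-sided 80% limits of 12%, 7.3% and 2.7% for ORR differences *d* of 20%, 15% and 10%, with 33 per arm. The control ORR is not stated, so it was solved for, using

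`d − z(0.80) × sqrt[pc(1−pc)/33 + pt(1−pt)/33]`, with `pt = pc + d`.

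- pc = 10%: 11.98%, 7.28%, 2.67%, which matches.
- pc = 5%: 12.9%, 8.3%, 3.9%, which does not.
- pc = 15%: 11.3%, 6.5%, 1.8%, which does not.

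In Section 10.1.4 (Part 2B), 80% Clopper-Pearson lower limits for 4/22, 3/22 and 2/22 are 8.17%, 5.12% and 2.44%, against the stated 8.2%, 5.1% and 2.4%. No stated figure is wrong. The problem lies in the definitions.

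**3. ORR difference in Part 2A**

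Assumptions: 0 to 4 of 33 undosed per arm; ORR among the treated of 10% on ipilimumab (the value inferred in step 2) and 25% on BMS-986218; undosed participants are non-responders. With `uI` and `uB` undosed on ipilimumab and BMS-986218:

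- Treated-set difference: 25% − 10% = 15.0 points, whatever the number undosed.
- Randomized-set difference: `0.25 × (33 − uB)/33 − 0.10 × (33 − uI)/33`.

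| Undosed ipilimumab | Undosed BMS-986218 | Randomized-set difference |
|---|---|---|
| 0 | 0 | 15.0 points |
| 0 | 4 | 0.25 × 29/33 − 0.10 = 12.0 points |
| 4 | 0 | 0.25 − 0.10 × 29/33 = 16.2 points |
| 4 | 4 | 0.15 × 29/33 = 13.2 points |

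Equal non-dosing only shrinks the difference in proportion. Unequal non-dosing can move it either way. For one arm with 8 responders and 3 undosed, ORR is 8/33 = 24.2% of randomized and 8/30 = 26.7% of treated.

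**4. PFS origin**

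For a dosed participant with no event before first dose, time from randomization is the lag plus time from first dose. Assume exponential PFS from first dose with a 12-week median (not a figure from the documents). The 24-week rate counted from first dose is 2^(−24/12) = 25.0%. Counted from randomization it is 2^(−23/12) = 26.5% with a 1-week lag and 2^(−22/12) = 28.1% with a 2-week lag. A lag common to both arms moves both the same way. A lag in one arm only would shift the PFSR difference by 1.5 to 3.1 points.

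**The case against.** The best defence is that the sentence specific to Parts 2A and 2B governs and the table wording is generic. The table serves six study parts, four of which do use treated participants. Section 10.3.1 plainly makes the treated analysis supplemental in Parts 2A and 2B. On that reading the intent is right and only the table wording lags behind. This is plausible, and it is why the point is an inconsistency and not a wrong choice of analysis. The table still gives no exception, and it holds the only definitions of ORR and PFS in the statistical section.

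A second defence is that Section 10.3 is a summary and the SAP will settle the matter before database lock. Only censoring is expressly deferred. Section 7.5 also gives designated sponsor personnel access to assignments before lock, so the definitions are better fixed now.

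Third, the stakes are limited. Section 3.2.1 says that no hypothesis is formally tested. Part 2A is preliminary, and the shifts in step 3 (−3.0 to +1.2 points) are small beside the 7.7-point distance from estimate to lower limit at a 15-point difference (15.0 − 7.3). That stands. An estimate nonetheless needs one denominator and one time origin.

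**Conclusion.** The conflict between Section 10.3.1 and Table 10.3.1-1 is certain on the wording, covers Parts 2A and 2B, and is not resolved elsewhere in the documents. Its effect on results is conditional. It requires that the table definitions are followed, and that some participants are randomized but not dosed or that the lag to first dose differs by arm. If everyone is dosed, ORR is the same on either set.

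Under the assumptions in step 3, a treated-set difference of 15.0 points corresponds to 12.0 to 16.2 points on the randomized set. That range holds the ORR among the treated fixed. If the participants who do not start differ in prognosis, the treated ORRs would move too.

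A reader might infer more, and the documents do not support it:

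- *That the plan has chosen a treated-set analysis and so breaks the randomized comparison.* It names the randomized population as primary and contradicts itself only in the table.
- *That Part 2B comparisons are biased.* No between-arm contrast is planned there.
- *That participants will decline ipilimumab because it is the older drug.* The documents do not say so, and Section 5.4.3 credits ipilimumab with a positive benefit-risk profile in melanoma. Non-starting could fall in either arm.

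**What to change.** In Table 10.3.1-1, add definitions for Parts 2A and 2B:

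- ORR over all randomized participants, counting the never-dosed as non-responders. Dosed but unassessed participants need no new rule, because they are already in the all-treated denominator.
- PFS from the randomization date. The censoring scheme promised for the SAP should cover participants who were never dosed.
- The treated-set ORR and first-dose PFS as the supplemental analysis already foreseen in Section 10.3.1.

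Also state in Sections 10.1.3 and 10.1.4 how never-dosed participants count toward the 33 and 22 per arm.

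This carries out what Section 10.3.1 already says. It also agrees with Appendix 5, Section 4.3.2, which dates stable disease from randomization in randomized trials. The cost is a change of wording and an ORR that may be slightly less favourable. No stated sample size or precision figure changes if all randomized participants are dosed.

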**Table 10.3.1-1: Efficacy - Statistical Analyses**

Endpoint	Statistical Analysis Methods
ORR is defined as the proportion of all treated participants whose BOR is either CR or PR by Investigator per RECIST v1.1 or per PCWG 3 criteria for prostate.  BOR for a participant will be assessed per RECIST v1.1 by Investigator, unless otherwise specified.	Estimate of ORR and corresponding 2-sided exact 95% CI using the Clopper-Pearson method by treatment for each tumor type.  For part 2A, estimate of difference in ORR between arms (using ipilimumab as reference) and corresponding 2-sided exact 95% CI using the Clopper-Pearson method by BMS treatment arms.
Median DOR  DOR for a participant with a BOR of CR or PR is defined as the time between the date of first response and the date of the first objectively documented tumor progression per RECIST v1.1 or per PCWG 3 criteria for prostate, or death, whichever occurs first.	Estimate by the Kaplan-Meier method and corresponding 2-sided 95% CI using Brookmeyer and Crowley methodology (using log-log transformation) by treatment for each tumor type.
PFSR at 24, 36, and 48 weeks  PFS for a participant is defined as the time from the first dosing date to the date of first objectively documented disease progression or death due to any cause, whichever occurs first.	Estimate PFSR by the Kaplan-Meier method and corresponding 2-sided 95% CI using Greenwood formula by treatment for each tumor type.  For part 2A, estimate difference in PFSR between arms (using ipilimumab as reference) by the Kaplan-Meier method and corresponding 2-sided 95% CI using Greenwood formula by BMS treatment arms.  Estimate median PFS by the Kaplan-Meier method and corresponding 2-sided 95% CI using Greenwood formula by treatment for each tumor type.

Abbreviations: BOR = best overall response; BMS = Bristol Myers Squibb; CI = confidence interval; CR = complete response; DOR = duration of response; ORR = objective response rate; PCWG 3 = Prostate Cancer Working Group; PFSR = progression-free survival rate; PR = partial response; RECIST = Response Evaluation Criteria in Solid Tumors.

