**Table 4-1: Objectives and Endpoints**

Objectives	Endpoints

Primary
 

• To characterize the safety, tolerability, and DLTs and to determine the MTD/RP2D of BMS-986218 administered as monotherapy and in combination with nivolumab in participants with advanced solid tumors

• To evaluate the efficacy and safety of BMS-986218 monotherapy relative to ipilimumab in participants with advanced cutaneous melanoma previously treated with anti-PD-1/PD-L1 immunotherapy (Part 2A only)

• To evaluate the efficacy and safety of BMS-986218 alone and in combination with nivolumab in NSCLC (Part 2B and Part 2C)

	

• Incidence of AEs, SAEs, AEs meeting protocol-defined DLT criteria, AEs leading to discontinuation, and death

• ORR, mDOR, and PFSR at 24, 36, and 48 weeks by RECIST v1.1

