#### **10.1.3    *The Randomized BMS-986218 Monotherapy Cohort Expansion in Cutaneous Melanoma (Part 2A)***

The primary purpose of the Randomized BMS-986218 Monotherapy Cohort Expansion in Cutaneous Melanoma (Part 2A) is to evaluate preliminary efficacy of BMS-986218 relative to ipilimumab 3 mg/kg. One hundred and thirty two response-evaluable participants will be randomized to BMS-986218 or ipilimumab evenly across study arms (eg, 33 participants to BMS-986218 at 7 mg Q4W; 33 participants to BMS-986218 at 20 mg Q4W; 33 participants to BMS-986218 at 70 mg Q4W; and 33 participants to ipilimumab) and stratified by the outcome (ie, progressed, relapsed) of previous anti-PD-1/PD-L1 immunotherapy. Additional response-evaluable participants may be randomized to further evaluate emerging data or subgroups of interest if needed but not to exceed 40 response-evaluable participants per arm. If additional participants are randomized, up to 160 response-evaluable participants (= 40 participants  $\times$  4 arms) may be randomized in Part 2A. The ORR of ipilimumab will serve as a control. With 33 treated participants in each BMS-986218 arm, the lower limit of the 1-sided 80% confidence interval for ORR difference from ipilimumab arm will be 12%, 7.3%, or 2.7%, assuming effect size of 20%, 15%, or 10%, respectively.

Although the above assumptions on the response rate were used for the purpose of sample size calculation, it should be noted that, to date, there are no anti-tumor response data available in this post anti-PD-1/PD-L1 population. The efficacy evaluation criteria may evolve by the time when the tumor data from this study are matured for evaluation.

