#### **10.1.4    *The BMS-986218 Cohort Expansion - Monotherapy (Part 2B)***

The purpose of the BMS-986218 Cohort Expansion - Monotherapy (Part 2B) is to gather additional safety, tolerability, preliminary efficacy as monotherapy, PK, and pharmacodynamic information. However, the sample size calculation will be based on the ORR.

The preliminary efficacy of BMS-986218 as a monotherapy in solid tumors, including NSCLC, in participants who have received, and then progressed on, relapsed, or have been intolerant to, at least 2 standard systemic therapies with proven survival benefit according to their tumor types for metastatic and/or unresectable disease will be evaluated. Sixty-six response-evaluable participants will be randomized evenly across study arms (eg, 22 participants to BMS-986218 at 7 mg Q4W; 22 participants to BMS-986218 at 20 mg Q4W; and 22 participants to BMS-986218 at 70 mg Q4W). Additional response-evaluable participants may be randomized to further evaluate emerging data or subgroups of interest if needed but not to exceed a total of 40 response-evaluable

participants per arm. If additional participants are randomized, up to 120 response-evaluable participants (= 40 participants  $\times$  3 arms) may be randomized in Part 2B.

With 22 treated participants in each BMS-986218 arm, the lower limit of the 2-sided 80% Clopper Pearson confidence interval for ORR estimate will be 8.2%, 5.1%, or 2.4%, assuming ORR estimate size of 18%, 13.6%, or 9.1%, respectively.

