### **4.3.2 Duration of Stable Disease**

SD is measured from the start of the treatment (in randomized trials, from date of randomization) until the criteria for progression are met, taking as reference the smallest sum on study (if the baseline sum is the smallest, this is the reference for calculation of PD).

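### Part 2A: the confidence interval for the ORR difference versus ipilimumab is assigned to Clopper-Pearson, a one-sample method that cannot produce it

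*Combined protocol and SAP*

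**What the plan says.** Table 4-1 makes the comparison with ipilimumab a primary objective of Part 2A: "To evaluate the efficacy and safety of BMS-986218 monotherapy relative to ipilimumab in participants with advanced cutaneous melanoma". ORR is among the endpoints listed for it.

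The ORR cell of Table 10.3.1-1 names Clopper-Pearson twice. The first use is for each treatment's own ORR. The second is for the Part 2A comparison: "estimate of difference in ORR between arms (using ipilimumab as reference) and corresponding 2-sided exact 95% CI using the Clopper-Pearson method".

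Section 10.1.3 also plans on an interval for this difference, but names no method: "the lower limit of the 1-sided 80% confidence interval for ORR difference from ipilimumab arm will be 12%, 7.3%, or 2.7" percent, for differences of 20, 15 and 10 points with 33 per arm. Sections 10.1.4 to 10.1.6 use Clopper-Pearson for single-arm rates only, for example "the lower limit of the 2-sided 80% Clopper Pearson confidence interval for ORR estimate will be 8.2%, 5.1%, or 2.4" percent in Part 2B.

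On the analysis set, Section 10.3.1 says the primary efficacy analyses "will be performed on the randomized population in Parts 2A, and 2B". Table 10.3.1-1 has "ORR is defined as the proportion of all treated participants whose BOR is either CR or PR by Investigator" and "PFS for a participant is defined as the time from the first dosing date".

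**The concern.** Clopper-Pearson inverts the tails of one binomial distribution, with one count and one sample size. A difference between two arms has two counts and an unknown common level (a nuisance parameter), and it can be negative. The method therefore has no output for this quantity. It looks as if the phrase was carried down from the single-arm sentence above it.

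This interval is the only measure of uncertainty that the table gives for the ORR comparison with the control arm. A programmer following the plan must substitute something, and the plan does not say what. The study is open-label, and Section 7.5 lets designated sponsor staff see assignments before database lock. A substitute chosen late could therefore be chosen with the results in view.

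The same table holds a smaller mismatch, for Parts 2A and 2B only. The primary analysis is on randomized participants, but the ORR row counts treated ones, and the PFS clock starts at first dose. A participant randomized but never dosed has no such date.

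**Working it through.** **1. The plan's own Part 2A limits fit a two-sample method.** Inputs from Section 10.1.3: n = 33 per arm; differences d of 20, 15 and 10 points; one-sided 80%, so z = 0.8416. The control ORR p is not stated; I assume 10%. The unpooled Wald lower limit is d - z × sqrt{[p(1-p) + (p+d)(1-p-d)]/33}:

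- d = 20: 0.20 - 0.8416 × sqrt[(0.09 + 0.21)/33] = 0.1198
- d = 15: 0.15 - 0.8416 × sqrt[(0.09 + 0.1875)/33] = 0.0728
- d = 10: 0.10 - 0.8416 × sqrt[(0.09 + 0.16)/33] = 0.0267

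These round to the stated 12%, 7.3% and 2.7%. A control rate of 5% gives 12.9, 8.3 and 3.9; 15% gives 11.3, 6.5 and 1.8. So the sample-size text is consistent with a two-sample interval and an ipilimumab ORR near 10%. That is an inference, not a stated value.

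**2. Clopper-Pearson is used correctly for single arms.** Two-sided 80% lower limits for 4, 3 and 2 responders of 22 are 8.2%, 5.1% and 2.4%, as in Section 10.1.4. For 4, 3 and 2 of 20 they are 9.0%, 5.6% and 2.7%, as in Section 10.1.6.

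**3. What it gives in Part 2A.** With illustrative counts of 10/33 and 3/33, the 95% output is two separate intervals: 15.6% to 48.7% and 1.9% to 24.3%. Subtracting opposite limits (15.6 - 24.3 and 48.7 - 1.9) gives -8.7 to 46.8, which is not a 95% interval for the difference.

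**4. What valid methods give.**

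- *Newcombe* combines the Wilson limits (l, u) of each arm: d - sqrt[(p1-l1)² + (u2-p2)²] and d + sqrt[(u1-p1)² + (p2-l2)²]. For 10/33 and 3/33 the Wilson intervals are 17.4% to 47.3% and 3.1% to 23.6%. The lower limit is 21.21 - sqrt(12.93² + 14.48²) = 21.21 - 19.41 = 1.8.
- *Miettinen-Nurminen* finds the differences at which the score statistic, with variance at the restricted maximum-likelihood estimates times N/(N-1), equals ±1.96.
- *Exact unconditional* inverts two one-sided 2.5% tests, maximised over the control rate. Outcomes are ordered by the score statistic or by the raw difference.

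95% intervals, in percentage points:

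| Counts | Difference | Miettinen-Nurminen | Newcombe | Exact, score | Exact, raw difference |
|---|---|---|---|---|---|
| 10/33 v 3/33 | 21.2 | 2.0 to 40.1 | 1.8 to 39.3 | 1.7 to 40.9 | -4.4 to 44.8 |
| 12/33 v 4/33 | 24.2 | 3.6 to 43.7 | 3.5 to 42.8 | 3.0 to 44.8 | -1.3 to 47.6 |
| 12/40 v 4/40 | 20.0 | 2.5 to 37.3 | 2.3 to 36.6 | 1.9 to 37.6 | -3.1 to 41.6 |

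Forty per arm is the cap in Section 10.1.3.

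**5. How often the choice matters.** I summed the two binomial distributions over all outcomes where two methods disagree on whether the lower limit exceeds 0. The true difference is 15 points, n = 33, and the control ORR is assumed:

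| Pair | Control 5% | 10% | 15% |
|---|---|---|---|
| Newcombe v Miettinen-Nurminen | 7.4% | 2.0% | 2.2% |
| Exact score v Miettinen-Nurminen | 5.5% | 1.3% | 0.1% |
| Exact score v exact raw difference | 34.9% | 23.0% | 15.2% |

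At n = 40 the last row is 42.1%, 25.8% and 16.7%. At a 10% control rate and n = 33, the chance that the lower limit exceeds 0 is 36.2% (Miettinen-Nurminen), 35.5% (Newcombe), 34.9% (exact score) and 12.0% (exact raw difference).

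**6. Denominator.** With 10 responders among 33 randomized, ORR is 10/33 = 30.3%. If 1, 2 or 3 were not dosed (assumed), the treated denominator gives 10/32 = 31.3%, 10/31 = 32.3% or 10/30 = 33.3%.

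**The case against.** The best defence is that this is a slip in a summary. Section 10.3 says a SAP will be finalized before database lock, and nobody can run Clopper-Pearson on a difference by accident. Section 3.2.1 disclaims formal hypothesis testing, and no rule depends on the sign of the lower limit, so step 5 measures a decision the plan does not make. Near the 10% control rate that the plan's own figures suggest, the sensible methods disagree in about 1% to 2% of trials. The large rates come only from the raw-difference exact interval, which no document names. Section 7.5 describes who sees assignments, not how methods are chosen.

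Most of this stands, and it limits the severity. It does not remove the error. Section 10.3.1 defers time-to-event censoring to the SAP but not the method for the ORR difference. A SAP that copies the row inherits an interval that cannot be computed, and one that departs from it conflicts with the protocol. The raw-difference result matters for one reason: it shows that the word *exact* alone does not define the interval.

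Two further objections have partial force. Part 2A randomization is stratified by the outcome of prior anti-PD-1/PD-L1 therapy, so the table should say whether strata enter the interval; an unstratified interval would still be sound. On PFS, Section 10.3.1 fixes the population but not the start date. The nearest text, Appendix 5, concerns stable disease: "SD is measured from the start of the treatment (in randomized trials, from date of randomization". It supports starting at randomization but does not require it for PFS.

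**Conclusion.** The concern holds. The method named for the Part 2A ORR difference is wrong as written, and nothing else in the protocol supplies a valid one. It should be fixed before Part 2A is analysed.

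The consequence is modest. Among Miettinen-Nurminen, Newcombe and the exact score interval, the limits in the examples differ by at most about 2 points. Only the raw-difference exact interval departs materially, by 4 to 6 points at the lower limit. Point estimates, single-arm intervals, the PFS-rate difference and the sample size are unaffected. The counts, control rates and numbers not dosed are illustrative assumptions; that Clopper-Pearson cannot give this interval depends on none of them.

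The mismatch between randomized and treated denominators in Parts 2A and 2B is real but minor.

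**What to change.** 1. In Table 10.3.1-1, replace Clopper-Pearson for the Part 2A ORR difference with one named two-sample 95% interval. Either use Miettinen-Nurminen or Newcombe and delete *exact*, or use an exact unconditional interval that inverts the score statistic and keep *exact*. State whether the randomization strata are used. Carry the same method into the SAP, and keep Clopper-Pearson for single-arm ORRs.
2. For Parts 2A and 2B only, define ORR over all randomized participants, and give PFS a start date that exists for participants randomized but not dosed. Randomization is the natural choice.

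Both should be settled before Part 2A results are analysed. The cost is wording in the protocol table and the SAP; sample size, randomization and data collection do not change. The trade-off in item 1 is small: the exact score interval is slightly wider (1.7 to 40.9 against 2.0 to 40.1 in the first example), while the other two give up the stated exactness.
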